### **3.3 Secondary Study Endpoints**

Secondary endpoints include:

1. Describe anti-tumor responses to CART-19 cell infusions.
  - a. For subjects with active disease, typical response criteria for partial response (PR) or complete response (CR) will be determined. Response determination will be only “descriptive” given the small number of subjects to be treated. The main endpoint for efficacy is Day 28 overall response rate. Other endpoints, including duration of remission, best overall response, CR/CRi with MRD negative bone marrow, RFS and EFS may also be summarized.
  - b. For subjects treated with MRD (identified by PCR analysis of blood or marrow), determine elimination of MRD scored as yes/no.
  - c. For subjects treated in remission, describe progression-free survival (PFS).
2. Describe overall survival and cause of death
3. For patients with stored or accessible tumor cells (such as patients with active CLL or ALL) determine if *in vitro* cell killing assays of CART-19 cells against patient tumor correlates with clinical response.
4. Determine if host immunity develops against the murine anti-CD19 or other elements of the transgene or vector such as VSV-G, and assess correlation with loss of detectable CART-19 (loss of engraftment).
5. In subjects infused with mixtures of CART-19 TCR $\zeta$  and TCR $\zeta$ :4-1BB cells, RT-PCR analysis of whole blood will be used to detect and quantify relative survival of CART-19 TCR $\zeta$  and TCR $\zeta$ :4-1BB cells over time.
6. Determine the relative subsets of CART-19 T cells (Tcm, Tem, and Treg)

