##### **4.4.2 Data Collection and Follow-up**

Follow-up data collection after cell therapy clinical trials is specified by the FDA. As long as patients have detectable cells transduced with the lentiviral vector, they should be followed for toxicity, immune reactions, and any long-term adverse events. Many patients who respond to cell therapy may also have prolonged DFS but are also at risk for late relapse. Therefore,

CONFIDENTIAL

subjects will continue to be followed for 1) engraftment as long as patients are at risk (until evidence of loss of detectable transduced T cells), 2) DFS until there is disease progression or they begin a new cancer therapy (except for HSCT); 3) survival until the time of death; or until the patient withdraws consent for clinical data collection or until two years after the last subject's infusion.

In the event that a subject cannot return to the study site for follow-up visits because of subject preference or geographical concerns, the subject's primary care physician and/or local oncologist may be asked to provide information from the subject's medical record to the study team at protocol defined timepoints (including the results of any routine care examinations and/or laboratory assessments), and assist in the collection of protocol required blood samples which will be sent to the University of Pennsylvania for protocol required analysis. The local provider will be contacted by a member of the study team to assess any potential toxicity. In numerous previous cell therapy trials at the CHOP and UPENN, loss of follow-up is estimated to occur in less than 5% of cases. Every effort will be made to contact subjects who appear to be lost to follow-up in order to at least obtain survival data. In the event a subject fails to complete the follow-up requirements, documentation of all attempts to contact the subject includes at least 3 telephone contacts (on different days and at different times of the day), and a certified letter.

After subjects' complete or prematurely discontinue participation in this study, subjects will also be asked to participate in a separate 15 year long-term follow-up destination protocol to further evaluate long term adverse events related to the study product.

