#### **6.9 Day 28 Evaluation**

PBMC will be obtained by a peripheral blood draw. Subjects will undergo the following: physical exam, documentation of adverse events and blood draws for hematology, chemistry, engraftment and persistence of CART-19 cells and research labs. In addition, restaging is done in order to provide tumor burden measurements. Restaging testing is determined by disease type and may include imaging, MRD assessments, lumbar puncture, bone marrow aspirate and biopsy and/or lymph node biopsy – these biopsies will be performed if necessary for determination of disease status and not for research. The day 28 evaluation may be repeated 28 days after the last infusion if the patient receives subsequent infusions.

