Observation and monitoring of patients will continue on a monthly basis until 24 weeks after a cell infusion is given. In subjects given a mixture of CART-19 cells, the change in the ratio of the vector transduced cells to each other between baseline and week four will be evaluated. After two years, annual follow-up for lentiviral vector safety will be carried out under a separate destination protocol for 15 years post infusion in accordance with FDA guidelines for retroviral vectors.

72 subjects will be targeted for infusion in this study. We have observed a drop out rate of less than 20% or less due to disease progression or clinical deterioration between enrollment and initial infusion (this will take about 6-8 weeks for screening-apheresis to dosing). However, as we are eliminating the test expansion, we may increase this dropout rate by 5-15%. Thus, up to 86 subjects will be initially enrolled to allow our goal of 72 infusions.

All safety data after initial CART-19 infusion will be summarized regardless of whether patient receives subsequent CART-19 infusions or not (Section 6.6). Efficacy data will be summarized from initial CART-19 infusion to first documented relapse or end of follow-up, whichever occurs first. Additional analyses may be planned as needed.

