### 7.2.2 Secondary Endpoints

- Describe anti-tumor responses to CART-19 cell infusions.
  - i. For subjects with active disease, typical response criteria for partial response (PR) or complete response (CR) will be determined. Response determination will be only “descriptive” given the small number of subjects to be treated.
  - ii. For subjects treated with MRD (identified by PCR analysis of blood or marrow), determine elimination of MRD scored as yes/no.
  - iii. For subjects treated in remission, describe progression-free survival (PFS).
- Describe overall survival and cause of death
- Rates of grade 2, 3 and 4 GVHD
- For patients with banked or accessible tumor cells (such as patients with active CLL, ALL, etc) determine if *in vitro* cell killing assays of CART-19 cells against patient tumor correlates with clinical response.
- Determine if host immunity develops against the murine anti-CD19, and assess correlation with loss of detectable CART-19 (loss of engraftment).
- For patients with stored or accessible tumor cells, evaluate the post infusion tumor response in comparison to baseline responses prior to cytoreductive chemotherapy (week -4), to evaluate the effect on general anti-tumor immunity.
- In subjects infused with mixtures of CART-19 TCR $\zeta$  and TCR $\zeta$ :4-1BB cells, RT-PCR analysis of whole blood will be used to detect and quantify relative survival of CART-19 TCR $\zeta$  and TCR $\zeta$ :4-1BB cells over time.
- Determine the relative subsets of CART-19 T cells (Tcm, Tem, and Treg)

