### **7.7 Statistical Analysis**

The statistical analysis will be primarily descriptive in keeping with the exploratory nature of the study. All adverse events will be described and exact 95% confidence intervals will be produced for adverse event rates, both overall and within major categories. The change in the ratio of CART-19 cells over time will be compared using a Wilcoxon signed-rank test for paired data. This nonparametric test is very efficient (>95%) compared to the t-test if the underlying data are normally distributed. Analysis of other secondary endpoints such as anti-tumor activity will also be primarily descriptive and may include summary statistics such as means and standard deviations or Kaplan-Meier curves for survival information. Descriptive statistics may also be summarized for the exploratory endpoint.

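### Section 7.1 ends the efficacy window at first relapse without exempting overall survival, and leaves it open through re-infusion in subjects who never respond

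*Combined protocol and SAP*

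**What the plan says.** Section 7.1 gives two adjacent reporting rules. For safety: "All safety data after initial CART-19 infusion will be summarized regardless of whether patient receives subsequent CART-19 infusions or not". For efficacy: "Efficacy data will be summarized from initial CART-19 infusion to first documented relapse or end of follow-up, whichever occurs first". The safety rule deals with re-infusion; the efficacy rule does not mention it. The only latitude offered is "Additional analyses may be planned as needed".

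The endpoints that this window could govern are:

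- Section 3.3, item 1: "The main endpoint for efficacy is Day 28 overall response rate". Best overall response, CR/CRi with an MRD-negative marrow, duration of remission, RFS and EFS are optional further summaries. PFS is listed for subjects treated in remission.
- Section 7.2.2, and item 2 of Section 3.3: "Describe overall survival and cause of death".
- Section 7.7: analysis of anti-tumor activity and other secondary endpoints "may include summary statistics such as means and standard deviations or Kaplan-Meier curves for survival information". No censoring rule is given.

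On follow-up, Section 4.4.2 continues "survival until the time of death", subject to consent and to a limit of two years after the last subject's infusion. Section 3.1 also plans overall survival follow-up, and Section 6.12 keeps relapsed subjects in follow-up for survival alone.

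On re-infusion, Sections 6.6 and 6.8 allow further infusions where there was no response. Section 15.1 then schedules a marrow 28 days after that infusion. Section 6.9 adds: "The day 28 evaluation may be repeated 28 days after the last infusion if the patient receives subsequent infusions". Section 6.14 also lists an assessment 28 days after the last infusion.

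**The concern.** One window is being asked to serve endpoints that need different ones.

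For response and time to relapse, stopping at relapse is natural. For overall survival it is not. If survival data stop at relapse, what remains describes death without relapse. Most deaths in a population without curative options may come after relapse, and these would be missing from the survival curve and from the cause-of-death table.

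For a subject who never responds, the problem is the reverse. Relapse cannot occur without a response, so only the end of follow-up closes the window. If that subject is re-infused and then responds, the response lies inside a window anchored on the initial infusion. A subject who relapses and is re-infused has already left the window. Second-course responses are thus counted only in subjects whose first course failed, which can only raise the reported rate.

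**Working it through.** The documents give no figure for the effect of this window, so there is nothing to reproduce. The check is one of text, followed by two illustrations in which every rate is assumed.

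**Text, side by side**

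| Question | Section 7.1 window | Rest of the plan |
|---|---|---|
| Does survival end at relapse? | Yes, if survival counts as efficacy data | No: 3.1, 4.4.2 and 6.12 follow survival beyond relapse |
| Is overall survival exempted? | Not stated | Not stated in 3.3, 7.2.2 or 7.7 |
| What closes the window in a non-responder? | End of follow-up only | Re-infusion and reassessment planned: 6.6, 6.8, 15.1 |
| Which Day 28 counts? | Not stated | 15.1 has one D28 (±4 days) column counted from Day 0; 6.9 and 6.14 allow a later repeat |

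**Illustration 1: overall survival**

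Assume constant monthly hazards: r for relapse, d for death without relapse, m for death after relapse. Assume also that the window would be applied as Kaplan-Meier censoring at relapse, which the plan does not state.

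- Survival counting all deaths: S(t) = exp(−(r+d)t) + r[exp(−mt) − exp(−(r+d)t)] / ((r+d) − m)
- Survival stopped at relapse: exp(−dt)

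Example: 50% relapse-free at 12 months (in the absence of death), 5% annual death without relapse, median survival after relapse 6 months.

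- r = −ln(0.50)/12 = 0.0578; d = −ln(0.95)/12 = 0.0043; m = ln(2)/6 = 0.1155
- At 24 months: exp(−(r+d)t) = 0.226 and exp(−mt) = 0.0625
- S(24) = 0.226 + 0.0578 × (0.0625 − 0.226)/(0.0620 − 0.1155) = 0.226 + 0.176 = 0.402
- Stopped at relapse: 0.95² = 0.902

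That is 40% against 90%. Other assumptions, 24-month survival counting all deaths, by median survival after relapse:

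| Relapse-free at 12 months | 5%/year, median 3 / 6 / 12 months | 10%/year, median 3 / 6 / 12 months |
|---|---|---|
| 40% | 21.6 / 32.4 / 49.7% | 19.5 / 29.8 / 46.5% |
| 50% | 30.1 / 40.2 / 55.5% | 27.2 / 36.8 / 51.5% |
| 60% | 39.9 / 48.8 / 61.7% | 36.0 / 44.4 / 56.8% |
| 70% | 50.8 / 58.1 / 68.3% | 45.8 / 52.6 / 62.4% |
| Stopped at relapse, every row | 90.2% | 81.0% |

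The overstatement runs from 81.0 − 62.4 = 19 points to 90.2 − 21.6 = 69 points.

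**Illustration 2: response after re-infusion**

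Apparent rate = [R + (72 − R) × share re-infused × response to re-infusion] / 72. The 72 infused come from Section 7.1; the rest is assumed.

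- R = 50 gives 50/72 = 69.4% for the initial course and 22 non-responders.
- Half re-infused (11), of whom 20% to 40% respond: 2.2 to 4.4 further responses.
- Apparent rate: 52.2/72 = 72.5% to 54.4/72 = 75.6%, an increase of 3 to 6 points.
- With initial response 50% to 90%, share re-infused 25% to 100% and response to re-infusion 20% to 40%, the increase runs from 0.5 to 20 points.

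**The case against.** A reader might infer that the plan drops deaths after relapse from overall survival. The documents do not support so flat a statement. They mostly use efficacy to mean anti-tumor response: Section 3.3 places its main efficacy endpoint and the related measures under item 1 and lists overall survival separately as item 2, and Section 7.5, headed Efficacy, never mentions survival. Section 4.4.2 gives disease-free survival and survival different stopping points. Following relapsed subjects for survival only would serve little purpose if survival stopped at relapse. This objection stands as evidence of intent. It does not supply the missing scope: Section 7.7 treats survival curves and anti-tumor activity together, and an open allowance for further analyses is not a prespecified exception.

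A reader might also infer that the main efficacy endpoint, Day 28 response, is inflated by second-course results. That too goes beyond the text. The schedule in Section 15.1 has one Day 28 column, counted from Day 0 and marked as the primary endpoint visit, and Sections 6.9 and 6.14 treat the later assessment as additional. Some exposure remains, because a further dose is possible from day 14 and the plan does not say how a dose before Day 28 is handled. The main exposure is in best overall response, MRD-negative CR/CRi and the duration endpoints that start from such a response.

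Three further points are fair:

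- The endpoint wording refers to infusions in the plural, so crediting re-infusion may be intended. If so, it should be stated.
- Part of Section 6.6 on subsequent infusions was not available for this review, so the absence of a rule is established only for the remaining text.
- A shift of 3 to 6 points is smaller than sampling error at 72 subjects: 1.96 × √(0.7 × 0.3/72) is about 11 points. But it acts in one direction only. The analyses are descriptive, so no error rate or power is affected.

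**Conclusion.** The point holds as a conflict between a stated reporting rule and the plan's own endpoints and follow-up, with moderate confidence. Section 7.1 does not exempt overall survival from a window that ends at relapse. For non-responders, the same window does not separate second-course responses from the initial course.

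The survival effect is potentially large, but only if the window is applied literally and as censoring at relapse. The 81% and 90% figures simply restate the assumed mortality without relapse. The response effect is modest in the central example and depends on how many non-responders are re-infused. None of these sizes predicts this trial's results.

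**What to change.** Amend Section 7.1 as follows:

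1. Limit the existing sentence to response and relapse-type endpoints: response, duration of remission, RFS, EFS and PFS.
2. Add that overall survival and cause of death are summarized from initial infusion to death or last contact, regardless of relapse, re-infusion or new therapy.
3. Add that Day 28 overall response uses the D28 (±4 days) assessment counted from Day 0, with any further dose given before that assessment flagged.
4. Add that responses first achieved after re-infusion for non-response are reported separately from best overall response to the initial course.

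The cost is a few sentences and no change to treatment. The assessments needed are already planned. One item should be checked: Section 6.12 and footnote 30 of Section 15.1 describe secondary follow-up only for subjects who leave the primary phase in remission, whereas Sections 3.1 and 4.4.2 set no such limit. The sponsor should confirm that survival status is collected for the others. The downside is that reported survival and response may look less favourable.

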### 7.2 Endpoints

#### 7.2.1 Primary Endpoints

- Monitor the occurrence of study related adverse events (defined as  $\geq$  Grade 3 signs/symptoms, laboratory toxicities, and clinical events) that are “possibly”,

CONFIDENTIAL

“likely”, or “definitely” related to study treatment any time from the first day of study treatment until week 24.

- Feasibility to manufacture CART-19 cells from patient apheresis products. The number of manufactured products that do not meet release criteria for vector transduction efficiency, T cell purity, viability, sterility and tumor contamination will be determined (defined as “manufacturing failures”).
- Duration of *in vivo* survival of CART-19 cells is defined as “engraftment”. PCR for CART-19 vector sequences will also be performed after infusion at 24 hours, weekly x 4, monthly x 6, and every 3 months thereafter until any 2 sequential tests are negative documenting loss of CART-19 cells.
- New onset secondary malignancies.

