#### **Exploratory objectives:**

1. Determine if insufficient in vitro T-cell test expansion in response to CD3/CD28 costimulation is predictive of manufacturing or clinical outcome.

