### **3.2 Primary Study Endpoints**

This phase I/IIa study is designed to test the safety and relative engraftment of the autologous T cells transduced with the anti-CD19 lentiviral vector in patients with relapsed, refractory and incurable CD19+ B cell malignancies.

Primary safety, feasibility and engraftment endpoints include:

1. Occurrence of study related adverse events, defined as NCI CTC  $\geq$  grade 3 signs/symptoms, laboratory toxicities and clinical events that are possible, likely or definitely related to study treatment at any time from the infusion until week 24. This will include infusional toxicity and any toxicity possibly related to the CART-19 cells including but not limited to:
  - a. Fevers
  - b. Capillary leak
  - c. Rash
  - d. Neutropenia, thrombocytopenia, anemia, marrow aplasia
  - e. Hepatic dysfunction
  - f. Pulmonary infiltrates or other pulmonary toxicity
  - g. Hypotension
  - h. In the allo cohort only, GVHD
2. Feasibility to manufacture CART-19 cells from patient apheresis products. The number of manufactured products that do not meet release criteria for vector transduction efficiency,

CONFIDENTIAL

T cell purity, viability, sterility and tumor contamination will be determined (defined as “manufacturing failures”).

3. Duration of *in vivo* survival of CART-19 cells is defined as “engraftment”. The primary engraftment endpoint is the # DNA vector copies per ml blood of CART-19 cells on week 4 after the first infusion. Q-PCR for CART-19 vector sequences will also be performed after each infusion, weekly x 4, monthly x 6, and every 3 months thereafter until any 2 sequential tests are negative documenting loss of CART-19 cells.
4. New onset secondary malignancies.

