#### **4.2 Exclusion Criteria**

1. Pregnant or lactating women. The safety of this therapy on unborn children is not known. Female study participants of reproductive potential must have a negative serum or urine pregnancy test performed within 48 hours before infusion.
2. Uncontrolled active infection.
3. Active hepatitis B or hepatitis C infection.
4. Concurrent use of systemic steroids at the time of cell infusion or cell collection, or a condition, in the treating physician's opinion, that is likely to require steroid therapy during collection or after infusion. Steroids for disease treatment at times other than cell collection or at the time of infusion are permitted. Use of inhaled steroids, or hydrocortisone for physiological replacement in patients with adrenal insufficiency are permitted as well.
5. ~~Presence of grade 2-4 acute or extensive chronic GVHD. See section 15.2 for definition of chronic GVHD. (NO LONGER APPLICABLE- Retired from V14)~~
6. ~~Under treatment for GVHD. (NO LONGER APPLICABLE- Retired from V14)~~
7. Previous treatment with any gene therapy products.
8. ~~Feasibility assessment during screening shows insufficient expansion in response to CD3/CD28 costimulation. (NO LONGER APPLICABLE – Retired from V11)~~
9. Any uncontrolled active medical disorder that would preclude participation as outlined.
10. HIV infection.

CONFIDENTIAL

11. [REDACTED]
12. CNS3 disease that is progressive on therapy, or with CNS parenchymal lesions that might increase the risk of CNS toxicity
13. Acute or chronic GVHD requiring systemic therapy (topical allowed).

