#### **4.3 Subject Recruitment and Screening**

Subjects will be identified through the clinical practices of the investigator or sub-investigators and through referrals from outside hospitals and physicians. No direct-to-patient advertising will be performed. The investigators will identify patients potentially meeting the study eligibility criteria through medical record reviews and the results of tests performed as part of routine clinical care. Subjects who are determined to be potentially eligible will be informed about the study. If the subject indicates willingness to participate in the study, the consent process will begin. Although many screening/eligibility tests are done routinely as part of standard oncology care, some are not, and written informed consent will be obtained before any non-SOC screening tests are conducted for research purposes. After informed consent has been obtained, the subjects will be evaluated for eligibility to ensure all inclusion and exclusion criteria are met. Eligible subjects will then be assigned a subject ID and considered enrolled by the sponsor. The test expansion (performed for exploratory purposes) will also occur in this phase. If and when the patient is eligible and enrolled with the sponsor, pheresis will occur if needed, and cell manufacturing begun.

The test expansion has been used to determine whether the subjects have an adequate number of T cells that can be successfully expanded with the anti-CD19 lentivirus vector, as determined from a sample of PBMC obtained by phlebotomy or prior apheresis at the first screening visit (~week -8).

Staggered enrollment on the CNS3 cohort: infusion of any subsequent patient on the CNS3 cohort will be delayed until 21 days after the prior CNS3 patient's infusion to allow for toxicity monitoring.

Female subjects of reproductive potential (women who have reached menarche or women who have not been post-menopausal for at least 24 consecutive months, i.e., who have had menses within the preceding 24 months, or have not undergone a sterilization procedure [hysterectomy or bilateral oophorectomy], or are not <11 years of age or who are not Tanner 1,) must have a negative serum or urine pregnancy test performed within 48 hours prior to entry.

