#### **4.4 Early Withdrawal of Subjects**

##### **4.4.1 When and How to Withdraw Subjects**

Subjects who do not complete the study protocol will be considered to have prematurely discontinued the study. The reasons for premature discontinuation (for example, voluntary withdrawal, toxicity, death) must be recorded on the case report form. Final study evaluations will be completed at the time of discontinuation. Potential reasons for premature discontinuation include:

1. The subject is lost to follow-up.
2. The judgment of the principal investigator that the patient is too ill to continue.
3. Pregnancy
4. Voluntary withdrawal; a patient may remove himself/herself from the study at any time without prejudice. A patient may withdraw from the study at any time they wish to withdraw consent.
5. Significant and rapid progression of malignancy, requiring alternative medical, radiation or surgical intervention including, but not limited to, the development of CNS metastasis.
6. Grade 3 or 4 toxicity, which is unmanageable, unexpected, unrelated to chemotherapy, and attributable to protocol therapy, or a serious adverse event that requires the subject's being withdrawn from the trial.
7. Technical difficulties are encountered in the T cell genetic modification and expansion procedure that precludes the generation of clinical cell doses that meet all Quality Control criteria outlined in Section 15.3.
8. Termination of the study by the principal investigator, the sponsor, the study funder, the IRB, or the Food and Drug Administration.

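### The primary manufacturing-feasibility count covers only products that miss five named release attributes, so failed expansion and insufficient cell yield fall outside it

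*Combined protocol and SAP*

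**What the plan says.** Section 3.2 item 2 names the endpoint as "Feasibility to manufacture CART-19 cells from patient apheresis products", and Section 7.2.1 repeats it. Both define the event in the same way, as "The number of manufactured products that do not meet release criteria for vector transduction efficiency, T cell purity, viability, sterility and tumor contamination". No denominator is given.

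Other passages bear on cell expansion and yield:

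- **Section 4.2, exclusion 8 (retired from V11):** subjects used to be excluded if "Feasibility assessment during screening shows insufficient expansion in response to CD3/CD28 costimulation".
- **Section 4.3:** "The test expansion has been used to determine whether the subjects have an adequate number of T cells that can be successfully expanded". The test is now exploratory.
- **Section 7.1:** "as we are eliminating the test expansion, we may increase this dropout rate by 5-15" per cent.
- **Section 4.4.1, item 7:** a subject may be discontinued when technical difficulty in genetic modification and expansion "precludes the generation of clinical cell doses that meet all Quality Control criteria". Discontinuation reasons go on the case report form.
- **Section 1.7, Feasibility:** manufacturing is not expected to be a problem, because the target dose should be comfortably exceeded.
- **Section 7.6:** the population for primary and secondary endpoints is all infused patients. Enrolled but uninfused patients form a second population. The comparison of enrolled with infused numbers is described as a measure of feasibility.

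**The concern.** The endpoint asks whether a usable product can be made from a patient's cells. There are at least three ways for that to fail: the culture does not grow, it grows but yields too few cells, or the finished product fails a release test. The definition captures only part of the third. The first gives no finished product to test. The second can give a product that passes all five named tests.

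The omitted routes are the ones that the retired screen was meant to detect. Section 1.7 also rests its own feasibility argument on cell yield, which the primary feasibility endpoint does not measure. An endpoint built this way can only err in one direction, towards calling manufacturing feasible.

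**Working it through.** **Step 1: which outcomes are counted.** The passages were set against the possible fates of a subject whose cells enter manufacturing.

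| Fate | In the 3.2 / 7.2.1 count? | Where else it appears |
|---|---|---|
| Product fails one of the five attributes | Yes | 7.6, enrolled versus infused |
| Culture stopped for insufficient expansion | No: no manufactured product to test | 4.4.1 item 7; 7.6 |
| Product passes all five but has too few cells | No: yield is not an attribute | 4.4.1 item 7; 7.6 |
| Product fails a release test outside the five | No | 5.4 shows that the list of release criteria is open-ended |

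**Step 2: whether another provision closes the gap.**

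- Section 7.6 compares enrolled with infused numbers, but this total combines manufacturing causes with progression, deterioration, death and withdrawal. The only manufacturing cause it lists is ineffective transduction.
- Section 7.6 also restricts the primary-endpoint population to infused patients. Read literally, that removes subjects who never obtained a usable product.
- Section 4.4.1 item 7 refers to Section 15.3 for quality-control criteria, but Section 15.3 is the monitoring plan.
- Section 7.1 makes the stopping rules the main basis for judging feasibility. The criteria in Section 8.4.1 contain no manufacturing-failure count. Section 8.4 allows termination for problems in cell product generation only at the investigators' discretion.

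**Step 3: the plan's own figure.** Section 3.1 gives 72 infused, 20% dropout and up to 86 enrolled. 72 × 1.20 = 86.4, which reproduces 86. (72 / 0.80 = 90; whether 86 is enough is a separate matter.) Here 86 serves only as an upper limit on manufacturing starts.

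**Step 4: illustrative size.** Two assumptions are needed that the documents do not make: 86 manufacturing starts, and all of the extra dropout being failed expansion. Section 7.1 does not say whether 5-15% is absolute or relative, so both readings are shown. Intervals are exact (Clopper-Pearson) 95% CIs.

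- *Absolute points:* 86 × 0.05 = 4.3 and 86 × 0.15 = 12.9, so about 4 to 13 subjects. 4/86 = 4.7% (CI 1.3-11.5%); 13/86 = 15.1% (CI 8.3-24.5%).
- *Relative to 20%:* 86 × 0.20 × 0.05 = 0.86 and 86 × 0.20 × 0.15 = 2.58, so about 1 to 3 subjects. 1/86 = 1.2% (CI 0.0-6.3%); 3/86 = 3.5% (CI 0.7-9.9%).

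**Step 5: the denominator.** If a failed culture is not a product, it leaves the denominator as well. On the absolute reading, 86 − 4 = 82 and 86 − 13 = 73 products remain. With a further assumption of 2 release failures, the narrow count gives 2/82 = 2.4% (CI 0.3-8.5%) to 2/73 = 2.7% (CI 0.3-9.5%). Counting all manufacturing failures over starts gives 6/86 = 7.0% (CI 2.6-14.6%) to 15/86 = 17.4% (CI 10.1-27.1%).

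**The case against.** The best defence is that these cases are not lost and little depends on the count. Section 4.4.1 requires the discontinuation reason to be recorded, Section 7.6 reports enrolled against infused with an open-ended list of reasons, the analysis is descriptive (Section 7.7), and no feasibility threshold is set. All of this is true. It shows that the data will exist and that no formal decision fails. It does not put these cases into the primary count, which is the figure likely to be reported as the manufacturing failure rate.

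The release-criteria table in Section 5.2.1 is not visible and may contain a cell-number criterion. That limits what can be said about practice. It does not change the endpoint, which names its five attributes without one.

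A reader might go further in four ways that the documents do not support:

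- *The sponsor expects 5-15% expansion failures.* Section 7.1 says only that dropout may rise, and does not give failed expansion as the reason. The link is an inference from the purpose of the test. Section 1.7 is optimistic about yield.
- *Dropping the screen was the latest eligibility change.* It was retired from V11; the GVHD exclusions 5 and 6 were retired from V14.
- *The endpoint would read 0 of 86.* The plan states no denominator and no number of manufacturing starts, and Step 5 shows that failed cultures would leave a product-based denominator.
- *The exploratory objective is undermined.* It is to "Determine if insufficient in vitro T-cell test expansion in response to CD3/CD28 costimulation is predictive of manufacturing or clinical outcome". Neither it nor the matching endpoint in Sections 3.4 and 7.2.3 is tied to the narrow definition, so failed expansion can be counted there.

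**Conclusion.** The point holds on the wording of Sections 3.2 and 7.2.1. Failed expansion, insufficient yield and any release failure outside the five attributes are not in the primary feasibility count, and Section 7.6 makes this worse by naming infused patients as the population. The bias is towards feasibility. That conclusion needs no assumption about frequency.

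The size is not known. The illustration runs from about 1 to about 13 omitted subjects, depending on how 5-15% is read, and it rests on 86 manufacturing starts and on attributing all the extra dropout to failed expansion. It shows that the omission could matter and is not a forecast. Since the cases remain traceable through discontinuation reasons, this is a correction that should be made to a primary endpoint definition, not a loss of data.

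**What to change.** In Section 3.2 item 2 and Section 7.2.1, define the event per subject, over all subjects whose cells entered manufacturing. A failure is any case in which, for a manufacturing reason, no released product sufficient for infusion under the protocol's own dosing and release provisions was obtained. Tabulate the reasons separately: insufficient expansion or terminated culture, insufficient yield, and failure of any release test. Report the rate with an exact 95% CI. In Section 7.6, state that this endpoint uses all manufacturing starts and not only infused patients.

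Insufficient yield needs a reference figure that the protocol itself states. The same dose range is called a goal in the Study Summary, a maximum in Section 1.2, an initial dose in Section 1.7, and an upper limit in Sections 5.3.1 and 6.6. No passage calls its lower end a minimum for release or infusion. The sponsor must reconcile these passages; no dose is proposed here. The Section 15.3 reference in Section 4.4.1 should be corrected at the same time.

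The cost is mainly redrafting, plus the dose reconciliation. Discontinuation reasons are already collected, though manufacturing starts must also be logged so that the denominator is known. The downside is that the reported failure rate may look less favourable.
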